## **Introduction**

The application of standard evidence-based prevention interventions can decrease the incidence of pressure injuries (PIs). However, the development of serious PIs in high-risk patients in the early postoperative period remains a significant clinical challenge. Following surgery, PIs that appear within 1 to 5 days are often deep-tissue pressure injuries (DTPIs) [1].

The etiology of DTPIs remains a topic of ongoing discussion among experts, and a comprehensive understanding of the underlying pathophysiological mechanisms has yet to be achieved. One commonly accepted hypothesis posits that the occurrence of DTPIs can be attributed to the application of pressure or shear stresses, or a combination thereof, resulting in cellular deformation and eventual necrosis. The DTPIs exhibit a distinctive complexity due to the co-occurrence of ischemia and mechanical stress, thereby expediting the consequent harm [2,3]

[figure not shown]
- 1 -

Title: Effectiveness of polyurethane foam (pink pad) compared with Mepilex dressing for pressure ulcer prevention in operating room

Version: 2.0 (20-Jun-2023)

Effective date: 15-Aug-2023

Expiration date: 15-Aug-2024

اللجنة المحلية لأخلاقيات البحث  
Institutional Review Board

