### **Objective measures**

#### **For the primary objective**

Pressure ulcer incidence will be assessed by using Bates–Jensen Wound Assessment Tool (BWAT) after operation then day 3 and day 7 for both treatments.

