### **Exclusion Criteria:**

- Subjects under 18
- Not consenting to participate
- Patients with suspected hypersensitivity reactions to any of the dressing formulation's ingredients.
- Patients who are unable to continue the study because of death or change in the care setting.

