## **Effectiveness of polyurethane foam dressing compared with Mepilex dressing for pressure ulcer prevention in operating room: A randomized control clinical trial.**

Prior to surgery, Mepilex Border Sacrum dressings 20 X 20 (Molnlycke Health Care) will be applied to the patient's sacrum for Mepilex Border Sacrum dressings group and polyurethane foam will be used to the patient's sacrum for polyurethane foam group. A nurse in the preoperative patient receiving area will apply the Mepilex Border Sacrum dressings. The perioperative nurse will examine the dressing in the operating room to ensure its integrity. If the perioperative nurse observed any alterations to the original application, such as rolling or displacement, she will reapply it. If the dressing is not applied by the nurse before transferring the patient to the operation room the perioperative nurse will apply it. For polyurethane foam (pink Pad) it will be used only by operating room nurses as it is available only in the operating room. Both types of intervention will be available in the operating room.

Patient will be examined by head nurse of wound management team after the operation then at day 3- and 7-days post operation. The dressing should be removed after 7 days post operation or if there is any clinical indication for removal. If a patient is discharged before 7 days post operation for any reason the head nurse of wound management team will examine the patient before discharge. Follow up will be for maximum 7 days post operation for each subject. Any patient will be unable to continue the study because of death or change in the care setting will be excluded from the study.

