#### **Section II: Pressure ulcer assessment.**

If there is any incidence of pressure ulcer this section will be recorded. The most common location for PI is the sacrum, which is particularly vulnerable to injury and difficult to treat . This section will be adopted from Bates-Jensen 2010 [27]. The Bates-Jensen Wound Assessment Tool (BWAT) will be used to assess pressure ulcers. It is a validated wound assessment tool which is used in many healthcare settings for wound assessment. BWAT is straight forward to use and allows nurses to have an objective, comprehensive assessment of wounds. It consists of 13 items to evaluate wound size, type and depth, amount of necrotic tissue, amount and characteristics of exudate, the presence of granulation tissue,

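### A patient who leaves before day 7 can fall under either the pre-discharge examination rule or the undefined change-of-care-setting exclusion, so examined, randomised patients may be dropped

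*Protocol*

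**What the plan says.** The primary outcome is pressure ulcer incidence, assessed "after operation then day 3 and day 7 for both treatments" (Protocol, Objective measures).

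The Study Procedure has two sentences about patients who leave early:

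- On discharge: "If a patient is discharged before 7 days post operation for any reason the head nurse of wound management team will examine the patient". This examination takes place ahead of the departure.
- Two sentences later, on leaving the study: "Any patient will be unable to continue the study because of death or change in the care setting will be excluded from the study".

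Between them stands the follow-up limit: "Follow up will be for maximum 7 days post operation for each subject". There is no minimum.

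The second rule also appears among the Exclusion Criteria, "Patients who are unable to continue the study because of death or change in the care setting", and again at the end of Section II of the data tool. Neither place defines a change of care setting or says whether discharge is one. The Setting section lists the operating room, the cardiac surgery intensive care unit and the cardiac surgery ward as the places where the study is carried out. The Blinding section says that the trial is open label and that the outcome assessor could not be blinded.

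**The concern.** A patient sent home or to another hospital on day 4 has been discharged before day 7, so the first rule applies and an examination is done. The same patient has also left the places where the study is run, so the second rule can be read to apply and the patient is excluded. The Protocol does not say which rule prevails, or whether the pre-discharge examination then counts towards the primary outcome.

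The exclusion acts after randomisation, on patients whose skin has already been examined at least once, and treatment is known to everyone. It removes them from both the numerator and the denominator of the primary incidence. If departures differ between arms, or are handled differently, the compared groups are no longer those that randomisation created. This is a rule about who stays in the trial, which the Protocol itself lays down. A statistical analysis plan could not recover examinations from patients already removed.

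**Working it through.** **1. The rules side by side**

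| Event before day 7 | Discharge sentence | Exclusion sentence |
|---|---|---|
| Discharge home | Applies, for any reason | Unclear: term undefined |
| Transfer to another hospital | Applies if the transfer is a discharge | Applies on a natural reading |
| Status in the analysis | Not stated | Excluded |

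At least the second event can meet both descriptions.

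**2. The plan's own figure**

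The Sample Size section gives N = 90, p = 0.5, d = 0.05, 99% confidence and a minimum of 79. With z = 2.576:

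n = N z² p(1−p) / [d²(N−1) + z² p(1−p)] = 90 × 1.659 / (0.2225 + 1.659) = 79.4.

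The figure is reproduced. It has no term for patients lost or excluded, and 80 are planned, so two exclusions take the trial below its stated minimum. It is a precision figure for one proportion and does not measure the bias discussed here.

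**3. Effect of excluding early leavers**

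Inputs: overall incidence I = 29.5%, which the Introduction cites as an upper figure; 40 patients per arm; share leaving early s and their incidence q, both assumed because the Protocol gives neither.

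Incidence after exclusion = (I − s q) / (1 − s). With q = 10%:

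| s | Calculation | Incidence | Left per arm |
|---|---|---|---|
| 10% | (0.295 − 0.010) / 0.90 | 31.7% | 36 |
| 20% | (0.295 − 0.020) / 0.80 | 34.4% | 32 |
| 30% | (0.295 − 0.030) / 0.70 | 37.9% | 28 |

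If early leavers carry the same risk as the others (q = 29.5%), the result stays at 29.5% for every s and only patients are lost.

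**4. What this could do to the comparison**

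Take the same true incidence of 29.5% in both arms, with q = 10%.

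- Same rule and same s in both arms: no difference is created.
- s = 30% in both arms, kept in one and excluded in the other: 37.9 − 29.5 = 8.4 points.
- Excluded in both, s = 10% in one and 30% in the other: 37.9 − 31.7 = 6.2 points.

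Keeping everyone does not remove all risk. Suppose 4 patients leave early in one arm and 12 in the other, all patients have a 29.5% risk, and none of the early leavers' ulcers is yet visible. The arms then show 36 × 0.295 / 40 = 26.6% and 28 × 0.295 / 40 = 20.7%, a spurious 5.9 points. If half are visible the gap is about 3 points (2.95), and if all are visible it is zero.

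**5. Cost of the shorter window if patients are kept**

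The Introduction says that injuries appearing on days 1 to 5 are often deep-tissue injuries, but gives no onset distribution. Assume uniform onset over those days. A last look on day 3 misses (5 − 3)/4 = 50%, on day 4 (5 − 4)/4 = 25%, and on day 5 nothing. With s = 30% and q = 10%, early leavers contribute 0.30 × 0.10 = 3 points of incidence. Missing 25% to 50% of that costs 0.75 to 1.5 points, giving 28.75% to 28.0% instead of 29.5%. Under these inputs, exclusion matters far more than the shortened window.

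**The case against.** The strongest reply is that the Protocol is coherent as it stands. Discharge has its own sentence, covering any reason. Follow-up is a maximum, so shorter follow-up is foreseen. The exclusion could be meant for other events. The Setting section says where the study is run and does not define a care setting. This reply stands in part. A reader might infer an outright contradiction, and the text does not go that far: it never says that discharge is a change of care setting. But it never says the opposite either, and a transfer to another hospital remains open under any reading.

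Other inferences go beyond the documents:

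- That a patient examined at discharge is then counted as ulcer-free to day 7. No section says so. It is a plausible result of the recording rule in Section II, "If there is any incidence of pressure ulcer this section will be recorded", together with the plan to report numbers and percentages. The handling of incomplete follow-up may be set in an analysis plan that is not shown.
- That staff who have just seen the skin choose the rule. The assessor is unblinded, but the Protocol does not say who decides on exclusion.
- That early discharge is common, linked to low risk, or different between arms. The Protocol gives no figure for any of these.

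**Conclusion.** The point holds as an unresolved overlap between two stated rules, one of which removes randomised patients after allocation. It should be corrected because it affects who is counted in the primary outcome of an open-label trial.

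Its size cannot be determined from the Protocol. The figures of 31.7%, 34.4% and 37.9% against 29.5% are illustrations. They rest on an incidence cited as an upper value, an assumed 10% among early leavers, and assumed departure shares of 10% to 30%. With equal risk in leavers and stayers, the shift in incidence is zero. Bias in the arm comparison further requires that departures, or their handling, differ by arm. The documents leave this possible but do not show that it will happen.

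**What to change.** Reconcile the Exclusion Criteria, the Study Procedure and the end of Section II:

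- State that discharge or transfer before day 7 is not a reason for exclusion from the analysis, and that every randomised patient's examinations up to departure count in the arm assigned.
- Record the date of the last examination for every patient, with or without an ulcer, and report days of observation by arm.
- Keep the incidence proportion as the main summary, and add a sensitivity comparison of findings up to day 3, the last scheduled examination before day 7.

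Kaplan-Meier with censoring at discharge should not replace the percentage as the main analysis. It assumes that discharge is unrelated to ulcer risk. If those who leave early are at lower risk, it gives them the later risk of those who stay and pushes incidence upwards, in the same direction as exclusion.

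The cost is a few sentences of Protocol text, one date per patient and one extra table. The exclusion for death stands in the same sentences and needs its own decision, which this point does not cover.

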## **Effectiveness of polyurethane foam dressing compared with Mepilex dressing for pressure ulcer prevention in operating room: A randomized control clinical trial.**

- Patient who has skin intact and having a life expectancy greater than 72 hours as per clinical judgement.

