### **Randomization**

Electronic randomization will be used as a simple technique of randomization. The randomization list was generated electronically using R and the Random Allocation Rule by a member of the research center who was not actively involved in the trial's enrollment and recruitment. A member of the research center will identify the participant for this concealment. To determine which treatment a participant will receive, an allocation sequence and envelopes containing the sequence will be generated. Each envelope will not be opened until the patient has consented and been enrolled in the study.

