## **Effectiveness of polyurethane foam dressing compared with Mepilex dressing for pressure ulcer prevention in operating room: A randomized control clinical trial.**

the study team to provide an overview of the study's implementation, with the aim of ensuring adherence to quality standards and regulatory requirements. Researchers will explain the study to the participants and take written consent if they want to participate. In cases where a patient is unconscious, written consent will be obtained from their Legally Acceptable Representative in accordance with legal protocols. Voluntary and anonymous participation will be ensured. In case of passing away the collected data will not be used, and safety reports will be submitted as per the local gaudiness. The data collection sheets will be securely stored in a locked file cabinet under the custody of the researchers.

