## **Effectiveness of polyurethane foam dressing compared with Mepilex dressing for pressure ulcer prevention in operating room: A randomized control clinical trial.**

epithelialization, and peri- 6 wound skin. PU length and width was measured with a disposable ruler and expressed as cm^2. The patient will be examined after operation then day 3 and day 7. Follow up will be for maximum 7 days post operation for each subject. If the any patient will be unable to continue the study because of death or change in the care setting the researcher will be excluded from the study.

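### Randomised patients who die are excluded and their recorded data barred from use, so pressure injuries already observed drop out of both objectives

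*Protocol*

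**What the plan says.** Three sections of the protocol remove patients because of death or a change of care setting:

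- Exclusion Criteria lists "Patients who are unable to continue the study because of death or change in the care setting".
- Study Procedure: "Any patient will be unable to continue the study because of death or change in the care setting will be excluded from the study".
- Study outcome measurement, Section II, has a garbled version: "because of death or change in the care setting the researcher will be excluded from the study". Read literally, it excludes the researcher; the patient is presumably meant.

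For deaths alone, Data Collection and Management goes further: "In case of passing away the collected data will not be used". The same section keeps the records: "The data collection sheets will be securely stored in a locked file cabinet under the custody of the researchers".

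The timing is set elsewhere. Under Randomization, "Each envelope will not be opened until the patient has consented and been enrolled in the study". Objective measures has pressure ulcer incidence assessed "after operation then day 3 and day 7 for both treatments". The inclusion criteria require the patient to be "having a life expectancy greater than 72 hours as per clinical judgement".

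**The concern.** A death during follow-up happens after allocation, so it cannot decide who was eligible. Used as an exclusion, it limits the analysis to survivors. The data ban also deletes outcomes that were actually observed, and pressure ulcer incidence is the measure for the comparison of the two products as well as for the overall estimate.

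The removed patients need not resemble those who stay. The Introduction names vascular disease and vasopressors after surgery as risk factors for injury, and patients who die plausibly share them, although the documents do not show this. The trial is also open label with an unblinded assessor, so an undefined change of care setting would be judged by people who may know the allocation.

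This is not a detail left to a later analysis plan. The protocol fixes the rule, and an SAP that analysed every randomised patient would contradict it.

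**Working it through.** **1. Order of events.** Consent and enrolment, then the envelope, surgery, and examinations after the operation, at day 3 and at day 7. A patient with an injury recorded at day 3 who dies on day 5 is randomised and has a known outcome, but is excluded under Study Procedure and has the record barred under Data Collection and Management. The eligibility criteria allow for such a death: follow-up is 7 × 24 = 168 hours after surgery and the life-expectancy floor is 72 hours. At least 168 − 72 = 96 hours lie beyond the floor, since it is judged before surgery. This says nothing about how many deaths to expect.

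**2. The plan's own figure.** Sample Size calculation gives population 90, expected frequency 50%, error 5%, confidence 99% and a minimum of 79. Check: n0 = z²p(1 − p)/d² = 2.576² × 0.25/0.0025 = 663.5, and n = 663.5/(1 + 663.5/90) = 79.25, which agrees. (Using n0 − 1 in the correction gives 79.36.) With 80 planned, two removals leave 78, below the protocol's own minimum. The finding does not depend on this.

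**3. False difference between arms.** No death or transfer rate is given, so the removals here are assumed. Take 40 per arm, x injuries in each arm (no true difference) and m removals per arm. In the extreme case all m removed patients were injured in one arm and none in the other:

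(x − m)/(40 − m) − x/(40 − m) = −m/(40 − m), whatever x is.

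- m = 1: 1/39 = 2.6 points.
- m = 2: 2/38 = 5.3 points.
- Removals alike in both arms: 0.

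These maxima hold only for an equal split. With 12/40 = 30% in each arm and four deaths in one arm only, of whom k had an injury, that arm shows (12 − k)/36: 33.3% for k = 0 down to 22.2% for k = 4. The false difference runs from +3.3 to −7.8 points.

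**4. Overall incidence.** With two removals per arm, 80 becomes 76. The result is (2x − 4)/76 if all four were injured and 2x/76 if none was.

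| True incidence | x per arm | All four injured | None injured |
|---|---|---|---|
| 10% | 4 | 4/76 = 5.3% | 8/76 = 10.5% |
| 20% | 8 | 12/76 = 15.8% | 16/76 = 21.1% |
| 30% | 12 | 20/76 = 26.3% | 24/76 = 31.6% |

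The last row is close to the Introduction's upper figure of 29.5% (0.295 × 40 = 11.8). If removed patients have the same injury rate as the rest, the estimate does not move.

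**5. What the recorded data are worth.** If all 80 are kept, only unknown outcomes widen the best/worst-case bounds on the risk difference, by 1/40 = 2.5 points each. The width is (removals − recorded injuries)/40. With four removals and 0, 1, 2, 3 or 4 recorded injuries it is 10, 7.5, 5, 2.5 or 0 points.

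**6. Change of care setting.** Exclusion is stated, but non-use of data is not. Pilot study uses the same phrase for patients left out of the trial, so removal from the analysis is the natural reading. Setting covers the operating room and the cardiac surgery ICU and ward, so a move among these is presumably not a change. Early discharge leaves those settings, yet Study Procedure provides an examination beforehand and states no exclusion. The two rules are not reconciled.

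**The case against.** The strongest reply concerns size. The number of deaths is unknown, and the illustrated bias is modest beside sampling error: with 40 per arm, the 95% half-width for the risk difference, 1.96 × √(2p(1 − p)/40), is about 13 points at 10% incidence, 17.5 at 20% and 20 at 30%. The 5.3-point extreme is roughly a quarter to two-fifths of that. This stands: a decisive effect on this trial is not shown. It does not justify the rule, because wide sampling error is no reason to discard observed events, and bias of this kind does not appear in the confidence interval.

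Second, the sentence barring the data goes on to require safety reports, so deaths are documented. True, but a safety report does not return the patient's pressure injury outcome to the analysis.

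Third, the care-setting part is weaker. The specific rule for early discharge can be read as governing, with those data used, which leaves an undefined phrase to clarify. That is fair; this part is an ambiguity, and the firm finding is the death rule.

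Fourth, arm-level disposition tables and sensitivity analyses commonly sit in an SAP. Agreed. Their absence is not the complaint; the stated exclusion and data ban are.

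**Conclusion.** The concern holds and must be fixed. Followed as written, the protocol removes randomised patients who die and forbids use of outcomes already recorded for them, in both the comparison and the incidence estimate. That conclusion rests on the text alone. The size and direction of the bias are unknown. The figures above rest on assumed removals: a false difference of 0 to 5.3 points with two per arm, +3.3 to −7.8 points with four in one arm at 30% incidence, and an overall incidence of 26.3% to 31.6% where the truth is 30%. A false difference between arms needs removals that differ in number or in injury status; the overall incidence can be biased even when they do not. For a change of care setting, exclusion is stated but the fate of the data is unclear.

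**What to change.** - Delete the death and change-of-setting item from Exclusion Criteria and the matching sentences in Study Procedure and in Study outcome measurement, Section II.
- Replace the data ban in Data Collection and Management, subject to the consent terms and ethics approval.
- State that all randomised patients are analysed in their allocated arm, and that any pressure injury recorded before death, transfer or discharge counts as an event.
- State how a patient who dies or leaves without an injury and without a day 7 examination enters the main analysis. Using the last examination has a drawback: an early death counts as injury-free, although the Introduction describes injuries appearing 1 to 5 days after surgery.
- Define a change of care setting and reconcile it with Setting and with the early-discharge provision.
- Report deaths and transfers by arm, with a best/worst-case table for patients whose outcome is unknown; the detail can go in the SAP.

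The cost is rewording in four places and one sensitivity table. No new data are needed, because examinations up to the event are already collected and the sheets are stored. An ethics amendment may be required, since the data ban sits beside the consent text and the consent pages are not available.
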